Study protocol. Statistical analysis and results.

Title: Identification of Epidural Space: A Comparison Study Between Contrast Spread and Loss of Resistance Techniques

REB tracking number: 19-06-002

Date of document: 07/17/2020

The study protocol.

The study participants were patients of Astoria Pain Management, New York, USA (age 28–72 years) with a clinical diagnosis of cervical radiculitis. The Canadian SHIELD Ethics Review Board approved this study (July 18, 2019. REB tracking number: 19-06-002), conducted from August 19, 2019, to October 8, 2019. Patients were eligible for the study if they met the criteria for cervical ESI, which included clinical and recent MRI findings confirming the diagnosis of cervical radiculitis and inadequate pain relief with conservative care for more than 3 months. Other criteria were if the procedure was covered by medical insurance, and if they signed informed consent. Patients were excluded from the study if they were taking anticoagulants or had serious comorbidities such as congestive heart failure.

The patients were divided into two groups of 20 each and underwent CESI with either an 18G or a 25G Tuohy needle. Patient selection for the18G and 25G groups was not random. For example, the preference was given for a 25G needle when the procedure was performed at the C5-6 level (25G/18G = 15/4) and for an 18G (18G/25G = 16/5) when the needle was inserted at C6-7 or C7-T1 level. The smaller needles were favored for females (25G/(25G+18G) = 17/24) vs. males (25G/(25G+18G) = 3/16). The skin was anesthetized with 1% lidocaine in the 18G group but not in the 25G group. All CESIs were performed utilizing the fluoroscopy only method when the needle was navigated from the skin toward the epidural space under contralateral obligue fluoroscopy, and the contrast spread technique was employed for epidural space identification. After radiological confirmation of the epidural spread, LOR was tested using an Epidrum® device (Exmoor Innovations Ltd., Somerset, UK). Subsequently, accompanied by the radiology assistant, I observed the Epidrum for 30 seconds or more; if the Epidrum deflated, the result was positive. However, if the device remained inflated, the result was reported as negative. The collected data was then analyzed.

Statistical analysis and Results.

There were three investigations:

1) Within group 1; 18G (LORT vs. CST),

2) Within group 2; 25G (LORT vs. CST); and

3) Between groups 1 and 2 (LORT 1 vs. LORT 2).

The Confidence Interval Test for Proportion to estimate the confidence interval (CI) between LORT and CST within groups 1 and 2 was employed. The 95% CI was [0.385, 0.815] for group 1 (LORT 60%; 18G) and [-0.031, 0.231] for group 2 (LORT 10%; 25G), confirming that LORT showed a statistically significant lower rate of epidural space detection than CST within each group (Table 1).

Table 1. The 95% Confidence Interval test for proportions of epidural space detection by LORT within 18G and 25G groups.

	Х	n	р	Margin of error for 95% Cl	Lower Limit	Upper Limit
LORT 18G	12	20	60	0.215	0.385	0.815
LORT 25G	2	20	10	0.131	-0.031	0.231

Rate of epidural space detection by CST in both groups is 100%. The 95% Confidence Interval test for proportions confirmed that epidural space detection by LORT is significantly lower than the CST. x–positive results, n–number of patients, p–percentage of positive results.

The z-test for independent proportions was utilized to compare the epidural space detection between LORT 1 (group 1; 18G) and LORT 2 (group 2; 25G). Since CST detected 100%, it was employed as a benchmark to conduct a hypothesis test of proportion, using H₀: ρ = 1; Ha: ρ < 1. There was a statistically significant difference between the proportions of epidural space detection by LORT with 18G compared to 25G needles: z = 3.31, p < 0.001, Cohen's h = 1.13 (Table 2).

Table 2. Z-test for independent proportions for the difference in the epidural space detection by LORT between 18G and 25G groups.

		Х	n	р	
LOR	T 18G	12	20	60	
LOR	T 25G	2	20	10	
Significance level	Pooled proportion	z	p-value	Effect size Cohen's h	
0.05	0.35	3.31	0.0009	1.13	

CST=20 (100%) was employed as a benchmark. Since p-value: 0.0009 < 0.05, H₀ was rejected. As Cohen's h > 0.8, the difference in LORT detection rate between 18G and 25G needles is large.

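### Epidrum deflation on needles already confirmed epidural by contrast is reported as the rate at which LORT detects the epidural space

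*Combined protocol and SAP*

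**What the plan says.** The document's title is "Identification of Epidural Space: A Comparison Study Between Contrast Spread and Loss of Resistance Techniques".

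Under the heading for the study protocol, the order of events is explicit.

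- Needle placement: "All CESIs were performed utilizing the fluoroscopy only method when the needle was navigated from the skin toward the epidural space".
- Identifying technique: "the contrast spread technique was employed for epidural space identification".
- LOR test: "After radiological confirmation of the epidural spread, LOR was tested using an Epidrum® device".
- Scoring: "I observed the Epidrum for 30 seconds or more; if the Epidrum deflated, the result was positive"; "if the device remained inflated, the result was reported as negative".
- Numbers: "The patients were divided into two groups of 20 each", one per needle gauge.

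Under the statistical analysis and results heading, the reading becomes LORT. Investigations 1 and 2 set LORT against CST within each gauge, and investigation 3 sets LORT with 18G against LORT with 25G. The text gives 60% and 10% for LORT and 100% for CST, "confirming that LORT showed a statistically significant lower rate of epidural space detection than CST within each group". The captions and notes of Tables 1 and 2 use the same detection language. The Epidrum is not mentioned anywhere in this section, nor is the fact that every reading followed contrast confirmation. No limit on generalising is stated.

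**The concern.** The methods and the conclusions describe different quantities. In the methods, contrast spread is the technique that identified the space, and LOR is a check made afterwards with one device. In the conclusions, LOR is a competing identification technique with a detection rate of its own.

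Someone using Tables 1 and 2 would take 60% and 10% as the rates at which LOR finds the cervical epidural space with 18G and 25G needles, and would conclude that LOR misses it in the rest. The documents link the Epidrum reading after confirmation neither to LOR used to find the space nor to any other way of testing LOR. The stated answer to investigations 1 and 2 therefore goes further than the data. The answer to investigation 3 is attached to the wrong endpoint name.

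**Working it through.** **1. Reproduce the stated figures.** Inputs from Tables 1 and 2: 12/20 for 18G and 2/20 for 25G.

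- Interval: p ± 1.96 × √(p(1 − p)/n).
  - 18G: 0.60 ± 1.96 × √(0.60 × 0.40/20) = 0.60 ± 0.215, giving 0.385 to 0.815.
  - 25G: 0.10 ± 1.96 × √(0.10 × 0.90/20) = 0.10 ± 0.131, giving −0.031 to 0.231.
- Pooled proportion: (12 + 2)/40 = 0.35.
- z = (0.60 − 0.10)/√(0.35 × 0.65 × 2/20) = 0.50/0.1508 = 3.31, two-sided p = 0.0009.
- Cohen's h = 2 arcsin√0.60 − 2 arcsin√0.10 = 1.772 − 0.644 = 1.13.

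All agree with the documents. The CST rate does not enter z, p or h. The arithmetic is not in question.

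**2. Ask what the proportions estimate.** Every reading was taken after contrast had shown epidural spread. The counts therefore estimate

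P(Epidrum deflates during the watch | placement confirmed by contrast, gauge),

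which is 12/20 = 0.60 for 18G and 2/20 = 0.10 for 25G.

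**3. Set methods beside conclusions.**

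| | Study protocol section | Statistical analysis and results section |
|---|---|---|
| What identified the space | Contrast spread | CST and LORT treated as rivals |
| When LOR was read | After epidural spread was confirmed | Not stated |
| Instrument | One device, the Epidrum | Not stated; called LORT |
| Meaning of a negative | Device stayed inflated on a confirmed placement | LORT failed to detect the space |

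**4. Follow the negatives.** There were 20 − 12 = 8 with 18G and 20 − 2 = 18 with 25G, 26 of 40 in all. Under the detection label these are 26 failures to find the space. In the methods they are 26 confirmed placements on which the device did not deflate.

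**5. Follow the comparator.** Because confirmed spread came before each LOR test, CST is positive by construction in everyone tested. The 100% is a condition for being tested, so setting 60% or 10% against it is not a head-to-head comparison of two ways of finding the space.

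No corrected figure can be computed. Nothing in the documents yields a rate for LOR as an identifying technique or for another LOR method.

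**The case against.** The best defence is disclosure. Device, timing and scoring rule are stated just before the investigations are listed, in a very short document, and the protocol itself calls the Epidrum check an LOR test. A reader of the whole can work out what LORT stands for. This stands as far as it goes, and it is why the remedy is wording. It does not rescue the conclusion, which concerns detection of the space and drops both the device and the condition.

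Some stronger readings are tempting and are not supported:

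- *That LOR was not measured at all, or that no loss was seen in any patient.* The device was watched over a period for a change of state, and 14 of 40 readings were positive. The documents give no definition of LOR that would exclude this test.
- *That no other LOR reading was taken.* The text describes none. The sequence makes one unlikely, but silence is not a statement.
- *That the title claims to cover every LOR method.* Its plural may simply count two techniques, CST and LOR.
- *That the 18G versus 25G test falls with the label.* Investigation 3 applies the same device and rule in both groups, and relabelling alters no count, z, p or h.

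**Conclusion.** The concern holds as one of endpoint labelling and scope. All 40 readings come from one device after contrast-confirmed placement, and all three investigations and both tables report them as LORT's detection of the space. The conclusion that LORT detects the space less often than CST exceeds what was measured and should not stand in that form. The gauge contrast, 60% against 10% with z = 3.31 and h = 1.13, stands as a contrast in Epidrum deflation. Keeping it does not settle how far the non-random choice of needle explains it, which is a separate matter.

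This rests on two assumptions: that the order of events in the methods applied to every patient, and that the absence of any other described LOR reading means none was used. The investigator can confirm both. The point does not depend on any outside definition of LOR. It matters because the headline claim changes, although no figure does.

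**What to change.** 1. In the investigations, table captions and conclusions, relabel the endpoint as *Epidrum deflation after contrast-confirmed epidural placement*. The title can stay.
2. In investigations 1 and 2 and Table 1, replace the LORT-versus-CST conclusion with the deflation proportion and its interval among confirmed placements: 12/20 = 60% (0.385 to 0.815) for 18G and 2/20 = 10% for 25G. The current 25G interval has an impossible lower limit of −0.031. Since the sentence is being rewritten, exact (Clopper-Pearson) limits could be used for both: 0.361 to 0.809 and 0.012 to 0.317.
3. Keep the 18G versus 25G test in Table 2 under the new label. The CST benchmark note there can go, as it plays no part in the test.
4. If the investigator confirms it, state that neither LOR as a means of identifying the space during advancement nor any other LOR method was assessed, so nothing is inferred about LORT in general.

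This needs no new patients or data. The cost is a narrower headline.

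### The 18G versus 25G comparison is an unadjusted z-test between non-randomly selected groups that differ in level, sex and skin lidocaine, so the large difference cannot be credited to gauge alone

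*Combined protocol and SAP*

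**What the plan says.** The allocation paragraph of The study protocol describes two groups of 20 and is open about how they arose: "Patient selection for the18G and 25G groups was not random". It gives two examples of the selection. On cervical level, "the preference was given for a 25G needle when the procedure was performed at the C5-6 level (25G/18G = 15/4"), and the reverse preference is recorded "for an 18G (18G/25G = 16/5) when the needle was inserted at C6-7 or C7-T1 level". On sex, "The smaller needles were favored for females (25G/(25G+18G) = 17/24) vs. males (25G/(25G+18G) = 3/16"). It also notes a procedural difference: "The skin was anesthetized with 1% lidocaine in the 18G group but not in the 25G group".

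Statistical analysis and Results lists the between-group comparison as the third of three investigations. The method is one two-sample test: "The z-test for independent proportions was utilized to compare the epidural space detection between LORT 1" (18G) and LORT 2 (25G). Table 2 reports 12/20 against 2/20, pooled proportion 0.35, z = 3.31, p = 0.0009 and Cohen's h = 1.13. Its footnote concludes that "the difference in LORT detection rate between 18G and 25G needles is large". The section describes no stratification, regression or matching, and does not mention the non-random selection again.

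**The concern.** A two-sample z-test isolates the effect of gauge only if the groups are otherwise comparable. Here the protocol itself reports that they differ on two characteristics counted for all 40 patients, and that a third feature, skin lidocaine, follows gauge exactly. Level and sex are introduced as examples, so other selection factors may exist.

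Any of these that influences whether the Epidrum deflates would be folded into the 50-point difference. The documents do not say whether they do, so confounding is possible but not demonstrated. Because loss-of-resistance results are not broken down by level or sex, a reader cannot tell whether the difference would shrink, hold or grow on adjustment. What is at stake is the interpretation of the third investigation: an effect of the needle, or an association between two selected groups.

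**Working it through.** **Inputs.** From the allocation paragraph: 20 patients per group; C5-6 in 4 (18G) and 15 (25G); C6-7 or C7-T1 in 16 and 5; women 24 − 17 = 7 and 17; men 16 − 3 = 13 and 3. The level and sex counts each sum to 20 per group. From Tables 1 and 2: 12/20 and 2/20 positives.

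**1. The plan's own figures.**
- z = (0.60 − 0.10)/√(0.35 × 0.65 × (1/20 + 1/20)) = 0.50/√0.02275 = 3.315; two-sided p = 0.00092.
- h = 2·arcsin√0.60 − 2·arcsin√0.10 = 1.772 − 0.644 = 1.129.

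These match Table 2. Fisher's exact test on the same counts gives p = 0.0022.

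**2. Link between gauge and the other factors.**
- Level: odds ratio (16 × 15)/(4 × 5) = 12; Fisher p = 0.0012.
- Sex: odds ratio (13 × 17)/(7 × 3) = 10.5; Fisher p = 0.0031.
- Lidocaine: 20/20 against 0/20, reading the sentence as applying to everyone in each group. Nothing can be estimated.

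**3. What adjustment could give.** The adjusted result cannot be computed, but it can be bounded. I took every way of dividing the 12 and the 2 positives over the two strata that fits the counts. For each I computed the Mantel-Haenszel risk difference, Σw(p18 − p25)/Σw with w = n18·n25/(n18 + n25), and the exact conditional two-sided p.

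| | By level | By sex |
|---|---|---|
| Compatible splits | 15 | 24 |
| Risk difference (crude 0.50) | 0.19 to 0.67 | 0.08 to 0.72 |
| Exact stratified p | 0.0002 to 0.28 | 0.00003 to 0.35 |
| Splits with p ≥ 0.05 | 6 | 9 |
| Weight of those splits if positives fall at random within gauge group | 9.7% | 2.1% |

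The smallest differences arise as follows.
- Level: weights 4 × 15/19 = 3.158 and 16 × 5/21 = 3.810. With 0/4 v 0/15 and 12/16 v 2/5, 3.810 × (0.75 − 0.40)/6.968 = 0.19 (95% CI −0.11 to 0.49).
- Sex: weights 7 × 17/24 = 4.958 and 13 × 3/16 = 2.4375. With 0/7 v 0/17 and 12/13 v 2/3, 2.4375 × (0.923 − 0.667)/7.396 = 0.08 (95% CI −0.11 to 0.28).

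The splits are not equally likely, and these extremes are corner cases. The joint level-by-sex counts are not given. The 5,970 joint tables that fit the margins span −0.17 to 1.00, with 57 at or below zero.

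**4. Largest share one factor could explain.** The crude risk ratio is 0.60/0.10 = 6.0. If gauge acts equally across strata, level alone can account for at most 0.80/0.25 = 3.2, leaving 6.0/3.2 = 1.9. Sex alone can account for at most 0.65/0.15 = 4.3, leaving 1.4.

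**5. If gauge had no effect.** The positive rates by level below are assumptions, not document figures. The probabilities are exact binomial results for the crude test with the stated level counts.

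| Assumed positive rate, C5-6 v below | Rejects at 0.05 | Reaches abs(z) ≥ 3.31 |
|---|---|---|
| 35% v 35% | 5% | 0.08% |
| 30% v 40% | 7% | 0.15% |
| 25% v 45% | 11% | 0.4% |
| 20% v 50% | 19% | 0.9% |
| 10% v 60% | 44% | 3.8% |
| 5% v 60% | 55% | 5.5% |

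A level effect could therefore inflate the error rate considerably, but would rarely produce a result as extreme as Table 2 by itself.

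**The case against.** The protocol discloses the non-random selection, the counts and the lidocaine difference, and nowhere says in terms that gauge caused the difference. The footnote attaches a conventional size label to h, and the label is correct for the observed proportions. Nothing in the documents links level, sex or skin lidocaine to deflation of the device.

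The numbers also give the plan some support. Every pooled single-factor estimate favours 18G, and a level effect alone rarely reaches z = 3.31. Counting splits is weak evidence: the count depends on the test (an uncorrected Cochran-Mantel-Haenszel test gives p > 0.05 in 3 of 15 and 6 of 24; with continuity correction, 6 and 12). The random-split weights reflect lost precision rather than confounding, because the mean adjusted difference under them is exactly 0.50. With 14 positives and cells of 3 to 5, adjusted estimates will be imprecise.

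All of this stands as a limit on the concern. It does not remove it. The disclosure never reaches the analysis or the conclusion, where the difference is stated as one between needles. The figures that would show whether adjustment matters were not reported, although level and sex were counted for everyone. Imprecision argues for modest modelling, not for leaving the crude result without a caveat.

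**Conclusion.** The concern holds and should be fixed. Table 2 is computed correctly and shows that the two observed groups differ; it does not show that gauge is the reason. Against a crude difference of 0.50, the published counts allow an adjusted difference of 0.19 to 0.67 by level or 0.08 to 0.72 by sex, with significance at 0.05 left open. These are bounds, not estimates, and a real gauge effect remains quite possible. The conclusion rests on the stated counts and on reading lidocaine use as complete in one group and absent in the other. It is confined to the third investigation.

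**What to change.** 1. Report loss-of-resistance positives by level and by sex within each gauge group, and the joint level-by-sex counts.
2. Add an exact stratified (conditional) test and a Mantel-Haenszel risk difference with 95% CI, by level and by sex separately. A joint exact or Firth logistic model should be supportive only, given 14 positives.
3. Label the crude z-test and Cohen's h as descriptive.
4. Word the Table 2 conclusion as an association between non-randomly selected groups. State that lidocaine use and any unrecorded selection factors cannot be separated from gauge, whatever the stratified result.

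The cost is re-tabulating and re-analysing data already collected and rewording one conclusion. The downside is wide intervals and possibly a less favourable p-value. If the difference persists after stratification, the finding is better supported than it is now.

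### Loss of resistance was read only after contrast had confirmed placement, so the data cannot show that it detects the epidural space less often than contrast spread

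*Combined protocol and SAP*

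**What the plan says.** The study protocol section of the Combined protocol and SAP describes one sequence for all patients. The needle was guided by fluoroscopy and "the contrast spread technique was employed for epidural space identification". The Epidrum came next: "After radiological confirmation of the epidural spread, LOR was tested using an Epidrum". The operator, with the radiology assistant, made the reading: "I observed the Epidrum for 30 seconds or more; if the Epidrum deflated, the result was positive". The section describes no third method of verifying placement, no LOR reading before or without positive contrast, and no blinding of the LOR reading to the contrast result.

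The Statistical analysis and Results section lists LORT vs. CST within each needle gauge as investigations 1 and 2. It says a one-proportion interval method "to estimate the confidence interval (CI) between LORT and CST within groups 1 and 2 was employed", and concludes from the two intervals, "confirming that LORT showed a statistically significant lower rate of epidural space detection than CST within each group". The Table 1 footnote states "Rate of epidural space detection by CST in both groups is 100" per cent, and repeats that "epidural space detection by LORT is significantly lower than the CST". The text before Table 2 gives the null as a proportion equal to 1, and the Table 2 footnote adds "CST=20 (100%) was employed as a benchmark".

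**The concern.** A positive contrast result was the condition for taking an LOR reading. In the patients analysed, a CST-negative, LOR-positive result could not occur, so LOR could tie with CST or score below it but never above it. A reference standard scores 100% against itself, and that 100% is not evidence of better detection.

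The title presents the study as a comparison of these two techniques, and investigations 1 and 2 are that comparison. A reader would take from them that CST has been shown to find the space at a significantly higher rate. The data answer a narrower question: how often the Epidrum deflates once contrast has already placed the needle in the space.

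**Working it through.** **Inputs.** From Tables 1 and 2: LOR positive in 12/20 (18G) and 2/20 (25G); CST 20/20 in each group. From the study protocol section: contrast first, LOR second.

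**1. The plan's figures reproduce.** Wald interval: p ± 1.96·√(p(1−p)/20).
- 18G: 0.60 ± 0.2147 = [0.385, 0.815].
- 25G: 0.10 ± 0.1315 = [−0.031, 0.231].

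Both match Table 1. The formula contains only the LOR count. It has no CST variability and no paired difference, so it is not an interval between the two techniques. CST enters only as a fixed 1.

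**2. The paired layout.**

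| Group | CST+ / LOR+ | CST+ / LOR− | CST− / LOR+ | CST− / LOR− |
|---|---|---|---|---|
| 18G | 12 | 20 − 12 = 8 | closed | closed |
| 25G | 2 | 20 − 2 = 18 | closed | closed |

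Discordant readings: 8 + 18 = 26 of 40, all in one direction. A paired test does not rescue the comparison. Exact McNemar gives 2·0.5^8 = 0.0078 and 2·0.5^18 = 0.0000076, but only because the opposite cell is closed. As an illustration with assumed counts that are not in the documents, 2 readings in that cell for 18G would give p = 0.11, and 8 for 25G would give p = 0.076.

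**3. What was and was not predetermined.** The direction was fixed; significance was not. Suppose *significantly lower* means that the Wald interval excludes 1. The documents do not state this rule, but it is how Table 1 is used. The intervals for 19/20 [0.854, 1.046], 18/20 [0.769, 1.031] and 17/20 [0.694, 1.006] include 1, and 16/20 [0.625, 0.975] is the first to exclude it. At least 4 misses in 20 are then needed. If the stated null of a proportion equal to 1 is taken literally, its variance is 0 and one miss rejects it.

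| Assumed true agreement of LOR with CST | P(tie, 20/20) = a^20 | P(≥4 misses), Wald reading | P(≥1 miss) = 1 − a^20, literal null |
|---|---|---|---|
| 99% | 82% | 0.004% | 18% |
| 95% | 36% | 1.6% | 64% |
| 90% | 12% | 13.3% | 88% |
| 80% | 1% | 58.9% | 99% |

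**4. CST's 100%.** If 20/20 is read as an observed success count, its exact (Clopper-Pearson) 95% CI is [83.2%, 100%], not a fixed 100%.

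**5. Effect of the missing reference.** Assume that k of the 8 Epidrum-negative 18G placements were not in fact epidural. Positivity among true placements is then 12/(20 − k): 60% at k = 0, 63% at k = 1, 67% at k = 2 and 75% at k = 4. The documents cannot determine k.

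**6. What the data do support.** Epidrum positivity given contrast confirmation, exact 95% CI: 18G 60% [36.1%, 80.9%]; 25G 10% [1.2%, 31.7%].

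**7. Table 2.** Pooled proportion (12 + 2)/40 = 0.35; z = 0.50/√(0.35·0.65·2/20) = 3.315; two-sided p = 0.00092. This reproduces the reported values without any CST data. It tests equality of the two gauges, so it cannot reject a null that the proportion equals 1.

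**The case against.** The order of the readings is disclosed and CST is called a benchmark, so an attentive reader can already see what 60% and 10% measure. The counts are sound and the shortfall is large. The exact upper limits for LOR (80.9% and 31.7%) lie below the lower limit of 83.2% for a 20/20 success count, so sampling error in CST alone would not overturn the contrast. The k scenario is assumed: nothing in the documents suggests that a contrast-confirmed placement was not epidural. At k = 4 the Wald upper limit for 12/16 is 0.962, still below 1. The four-miss rule is inferred, and the tie probabilities limit the concern rather than measure its harm. The absence of an independent reference is read from the silence of a short document.

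Much of this stands. Epidrum positivity below 100% at contrast-confirmed positions is well supported, and the k values show only how the estimate would move. None of it restores a ranking of the techniques. Disclosing the order does not open the closed cell, and non-overlapping intervals do not help when one of the two rates is the reference itself. If no patient lacked contrast confirmation, 20/20 is an observed count, but it remains unverified.

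**Conclusion.** The concern holds. The statements in the results text and the Table 1 footnote that LOR is significantly lower than CST are not supported as a comparison of two techniques. LOR exceeding CST had probability 0 by design, and all 26 discordant readings could fall only one way. The 8 and 18 negative Epidrum readings are real; what fails is the comparative significance claim. CST accuracy and LOR specificity cannot be estimated, and no corrected LOR versus CST figure can be computed from these data.

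This rests on the sequence as described and on no independent placement reference being described. Whether anyone without contrast confirmation was left out is unknown. Investigation 3 compares LOR with LOR, so its counts and z-test do not depend on CST's rate and are not affected by this point.

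**What to change.** **Main change.**
- Restate investigations 1 and 2 as the proportion Epidrum-positive among CST-confirmed epidural placements, with the needle already placed and the reading taken after contrast. Report it by gauge with exact 95% CIs: 18G 60% [36.1%, 80.9%]; 25G 10% [1.2%, 31.7%].
- Delete both statements that LOR is significantly lower than CST, in the results text and in the Table 1 footnote. Delete the description of the interval as lying between the two techniques.
- State that CST is the reference standard, and that CST accuracy and LOR specificity were not estimable.
- State whether any patient without contrast confirmation was left out of the 20 per group.

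**Separate, smaller change.** State Table 2's null as equal Epidrum-positive proportions with 18G and 25G, and drop the benchmark hypothesis there.

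**Cost.** Rewording of completed results: two sentences, the Table 1 footnote and intervals, the null at Table 2, and short statements on the reference standard and exclusions. No new patients, procedures or data are needed. The price is withdrawing the claim that CST detects the space at a significantly higher rate.

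### CST is 100% by construction among the procedures scored, so it cannot be verified as a success rate among attempts or used as a measured rival to LOR

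*Combined protocol and SAP*

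**What the plan says.** All references are to the combined protocol and SAP.

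Under The study protocol:
- Groups: "The patients were divided into two groups of 20 each and underwent CESI with either an 18G or a 25G Tuohy needle". On allocation: "Patient selection for the18G and 25G groups was not random".
- In all procedures "the contrast spread technique was employed for epidural space identification".
- The order of the two tests is explicit: "After radiological confirmation of the epidural spread, LOR was tested using an Epidrum® device".
- Two outcomes are defined: "if the Epidrum deflated, the result was positive", and "However, if the device remained inflated, the result was reported as negative".

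Under Statistical analysis and Results:
- The Table 1 note gives CST as a result: "Rate of epidural space detection by CST in both groups is 100" per cent. It defines n as the number of patients.
- The z-test paragraph adds: "Since CST detected 100%, it was employed as a benchmark to conduct a hypothesis test of proportion", with a null value of ρ = 1 and a one-sided alternative. The Table 2 note repeats the benchmark as 20 (100%).
- LOR was positive in 12/20 (18G) and 2/20 (25G). From the two confidence intervals the text concludes that LOR detects the space significantly less often than CST within each group.

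The documents give no number of procedures attempted, no number stopped or unconfirmed, no mention of a needle change, and no rule for counting any of these.

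**The concern.** LOR is tested only once contrast has shown epidural spread, and every result is a reading of the Epidrum. A procedure without confirmed spread has no result to record. Among scored procedures CST cannot fail, whatever its true performance, while LOR can. Investigations 1 and 2 then compare a proportion that was free to vary with one that the scoring rule holds at 1.00, and present the difference as one between two detection rates.

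This is separate from whether contrast spread is a good reference standard. Even if contrast were a perfect indicator of needle position, the reader would still not know how many attempts lie behind each group of 20.

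At stake is the main within-group conclusion. The figures 60% and 10% show how often the Epidrum deflated once contrast had confirmed placement. They do not show how often LOR would find the space compared with how often CST finds it. In investigation 3 there is a further possibility: the operator chose the needle, so any stopping or switching might have differed between gauges.

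**Working it through.** **Inputs.** LOR 12/20 (18G) and 2/20 (25G), from Tables 1 and 2. CST 20/20 per group, from the Table 1 and Table 2 notes. By level, 25G has 15 + 5 = 20 patients and 18G has 4 + 16 = 20; by sex, 25G has 17 + 3 = 20 and 18G has 7 + 13 = 20 (study protocol section). These counts close, but they describe the patients counted, not the procedures attempted.

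**1. The plan's own figures reproduce.**
- Interval p ± 1.96·√(p(1−p)/n). For 12/20: 0.60 ± 0.215 = [0.385, 0.815]. For 2/20: 0.10 ± 0.131 = [−0.031, 0.231].
- Pooled proportion 14/40 = 0.35; z = 0.50/√(0.35 × 0.65 × 2/20) = 3.315; two-sided p = 0.0009; h = 1.13.

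The z statistic uses only 12, 2, 20 and 20. The CST benchmark does not enter it, so the benchmark bears on investigations 1 and 2 only.

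**2. What the scoring rule can produce.**

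| Contrast | LOR tested? | Scored as |
|---|---|---|
| Spread confirmed | Yes | CST positive; LOR positive or negative |
| Spread not confirmed, or procedure stopped | No | No category defined |

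Only the first row can yield a result, so CST is 100% among scored procedures for any true success rate.

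**3. CST among attempts.** Assume k unrecorded unconfirmed or stopped attempts in a group. The documents do not give k, and it may be zero. CST = 20/(20 + k):

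| k | CST | Exact 95% CI |
|---|---|---|
| 0 | 100% | 83.2% to 100% |
| 1 | 95.2% | 76.2% to 99.9% |
| 2 | 90.9% | 70.8% to 98.9% |
| 3 | 87.0% | 66.4% to 97.2% |
| 5 | 80.0% | 59.3% to 93.2% |

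For k = 0 the lower limit is 0.025^(1/20) = 0.832. That limit reflects sampling precision, which a fixed benchmark of 1 ignores; it is not evidence of lost attempts.

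**4. Stress test of investigation 3: failures.** Add k attempts to the 18G group only, all scored LOR-negative. Two-sided z-test p = 0.0015 (k = 1), 0.0032 (k = 3) and 0.0062 (k = 5). It first exceeds 0.05 at k = 16 (12/36 against 2/20, p = 0.053). Fisher's exact test, p = 0.0022 on the reported data, first exceeds 0.05 at k = 12.

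**5. Stress test of investigation 3: switches.** Suppose j LOR-positive patients counted as 18G had started with 25G. LOR was never tested with their first needle, so two scorings are possible:

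| j | Result follows the patient | p | Scored LOR-negative with 25G | p |
|---|---|---|---|---|
| 1 | 11/19 v 3/21 | 0.0039 | 11/19 v 2/21 | 0.0011 |
| 2 | 10/18 v 4/22 | 0.014 | 10/18 v 2/22 | 0.0014 |
| 3 | 9/17 v 5/23 | 0.041 | 9/17 v 2/23 | 0.0019 |
| 4 | 8/16 v 6/24 | 0.104 | 8/16 v 2/24 | 0.0029 |

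At j = 3 the gap is 52.9 − 21.7 = 31 points under the first scoring and 52.9 − 8.7 = 44 points under the second. If three switched patients had all been LOR-negative, it would be 12/17 − 2/23 = 70.6 − 8.7 = 62 points. Three switches could therefore put the reported 50-point gap anywhere from 31 to 62.

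**The case against.** The strongest reply is that the documents mention no stopped, unconfirmed or switched procedure. The group sentence can be read as allocation first and procedure second, n is defined as patients, and the level and sex counts close at 20 + 20. If those 40 were everyone attempted, 20/20 per group is a genuine observed count. This stands, and it limits the point to what cannot be verified.

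A reader might infer that failed attempts were left out, or that patients were grouped by the needle finally used. No text supports either. The documents do not say whether the group means the first or the last needle.

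Second, for the sensitivity of LOR, contrast-confirmed placements are the natural denominator. If the needle is not in the epidural space, absence of epidural spread is a correct negative and not a CST miss. This also stands. Stopped or switched attempts should not automatically be scored as CST failures, and unconfirmed attempts should not be added to the LOR denominator as though that were a correction. The failure stress test above does so only to find a breaking point.

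Third, unconfirmed attempts scored negative on both methods would add no discordant pairs: the split stays at 8 to 0 (18G) and 18 to 0 (25G). This is true, but it does not rescue the comparison. The zero is itself a product of testing LOR only after confirmation, because a LOR-positive, CST-negative result could not be recorded.

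**Conclusion.** The point holds as one about what the 100% can mean. Among scored procedures CST is fixed at 100%. As a success rate among attempts it cannot be verified, and it should not stand as a measured rival rate (ρ = 1) in investigations 1 and 2. If all 40 attempts were confirmed, the supportable statement is 20/20 per group with an exact 95% interval of 83.2% to 100%. Under an assumed one to five unrecorded failures in a group, CST would be 95.2% to 80.0%.

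A reader might go further and conclude that the 18G–25G difference is biased. The documents do not support that. Needle choice did follow level (C5-6 in 15 of 20 for 25G and 4 of 20 for 18G), but that imbalance is confounding, and nothing links level to stopping or switching. Significance survives small numbers of unrecorded 18G failures. Losing it through switches takes about four LOR-positive patients, a third of the 12 positives, all keeping their positive result under 25G. Bias in investigation 3 remains only a possibility.

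**What to change.** 1. From the practice's procedure records for August 19 to October 8, 2019, report for each initially chosen needle the number attempted, confirmed, stopped or unconfirmed (with the reason), and switched.
2. Give CST as confirmed/attempted per needle with an exact 95% interval. If there were no other attempts, say so and state 20/20 (83.2% to 100%).
3. Describe 12/20 and 2/20 as LOR positivity given contrast-confirmed placement, and reword the conclusion that LOR detects significantly less often than CST to match.
4. If any switches are found, add a sensitivity analysis of the 18G–25G comparison by first needle, showing both LOR scorings of the switched patients.
5. If the records cannot establish the number attempted, state that 100% holds by construction among scored procedures, and withdraw it as a finding and as a benchmark.

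The cost is a review of about seven weeks of records at one practice and a few lines of re-analysis, with no new patients or procedures. The downside is that the CST figure may fall below 100% and the LOR-versus-CST conclusion becomes weaker.
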